Objective	To evaluate real-world outcomes for the SAPIEN 3 Ultra Transcatheter Heart Valve (THV) System in transcatheter aortic valve implantation (TAVI) centres that are implementing minimalist periprocedural practices and facilitating early discharge home
Device	Edwards SAPIEN 3 Ultra THV System
Study Design	Prospective, observational, single-arm, multicentre, post-market study
Subject Population	Subjects who will undergo TAVI with the Edwards SAPIEN 3 Ultra System as part of standard-of-care treatment.
Sample Size	Up to 500 subjects will be enrolled
Study Sites	Up to 50 centres predominantly in the European Union
Data Collection Schedule	Clinical data and imaging available from routine clinical assessments performed pre-procedure and through 1-year post-procedure will be collected.
Outcome Measures	
The following outcomes will be reported:
 
• Death• Stroke• New requirement for permanent pacemaker• Aortic valve reintervention• Valve haemodynamics
◦ Aortic regurgitation◦ Mean aortic valve gradient◦ Effective orifice area• Length of index hospitalization• Discharge location
Inclusion Criteria	
1. Will undergo TAVI with the Edwards SAPIEN 3 Ultra System as part of standard-of-care treatment2. Less than 80 years of age at time of the procedure3. Low surgical risk as determined by the Heart Team4. Meets clinical and procedural requirements for early discharge as determined by the Heart Team

5. The subject has been informed of the nature of the study, agrees to its provisions and has provided written informed consent

Exclusion Criteria

1. Medical, social, or psychological conditions that preclude appropriate consent and follow-up, including subjects under guardianship
2. Considered to be part of a vulnerable population
3. Active SARS-CoV-2 infection (Coronavirus-19 [COVID-19]) or previously diagnosed with COVID-19 with sequelae that could confound endpoint assessments
4. Cannot tolerate an anticoagulation/antiplatelet regimen
5. Active bacterial endocarditis
6. Participating in a drug or device study that has not reached its primary endpoint. Note: Participation in required national registries is not an exclusion.

Statistical Analysis

No statistical hypothesis testing will be performed. Only descriptive and summary statistical analysis will be provided for baseline/pre-procedure, procedure and outcome variables.

Sponsor

Edwards Lifesciences LLC

1 INTRODUCTION

Transcatheter aortic valve implantation (TAVI) is an established treatment for patients with severe aortic stenosis and has been performed for over a decade, however, there are currently no recommendations for the duration of post-procedure monitoring for patients undergoing TAVI and practices vary widely by institution and country.

Several studies have evaluated minimalist periprocedural approaches based on individual patient risk and criteria-driven discharge in order to standardize post-procedure care and reduce length of stay; these approaches also ultimately maximize the efficiency of hospital resources. In the European FAST-TAVI trial, a set of pre-specified discharge criteria established to allow safe and timely discharge were applied to a group of patients undergoing TAVI with the SAPIEN 3 transcatheter heart valve (THV) and 30-day outcomes were evaluated. A total of 328 patients had a low risk of complications and were discharged between 1- and 3-days post procedure.¹ Similarly, the 3M TAVR study evaluated the safety, effectiveness and feasibility of next-day discharge in patients undergoing balloon-expandable transfemoral TAVI when implementing objective pre-procedural screening criteria and standardized peri- and post-procedural management guidelines. A total of 411 patients with a mean age of 84 years and STS score of 4.9% had a median length of stay of 1.0 days, with next-day discharge achieved in 80.1% of patients and 89.5% discharged within 48 hours of the procedure.² The discharge criteria used in these studies are shown in **Table 1**; thirty-day outcomes are shown in **Table 2**. Both studies concluded that the event rates compare favourably with other recent trials and, thus, have demonstrated that early discharge home is safe and feasible for selected patients.

Table 1. FAST-TAVI and 3M TAVR Study Discharge Criteria

FAST-TAVI ¹	3M TAVR Study ²

NYHA Class ≤IIno chest pain attributable to cardiac ischaemiano untreated major arrhythmiaspatients having complications on day 0 to 1, but free of signs or symptoms on day 3no fever during the last 24 hours and no signs of an infectious causeindependent mobilisation and self-caringpreserved diuresis (>40 ml/hour during the preceding 24 hours)no unresolved AKI type 3 (according to VARC-2 criteria)no RBC transfusion during the preceding 72 hoursstable haemoglobin in two consecutive samples (defined as a decrease of no more than 2 mg/dl)no paravalvular leak (PVL) with aortic regurgitation less than moderateno stroke/transient ischaemic attack (TIA)no haemodynamic instability	
Monitoring
 
Completion and review of post-procedure transthoracic echocardiogram to confirm acceptable bioprosthetic haemodynamic with the absence of delayed complicationsAbsence of persistent intraventricular conduction delayAbsence of vascular access site complicationsAbsence of laboratory contraindications. If Hgb <100 g/L and eGFR <30 mL/min, obtain and review outpatient bloodwork 2 and 4 d after dischargeFacilitated reconditioningReturn to baseline mobilizationAbsence of elimination issues (e.g., urinary retention) 
Communication
 
Multidisciplinary agreement of safety of dischargeConfirmation of discharge plan with patient/familyConfirmation of availability of social support during the initial 48 h after dischargeCompletion of verbal discharge teaching and confirmation of patients/family's understanding of the discharge guidelines and provision of written discharge education resources and prescription of medications

Table 2. FAST-TAVI and 3M TAVR Study 30-Day Outcomes (%)

Outcome	FAST-TAVI ¹	3M TAVR Study ²
Mortality	0.6	1.5
Stroke	0	1.5
Permanent pacemaker	4.3	5.7
Cardiac rehospitalization	3.4	5.7

2 STUDY OBJECTIVE

The SAPIEN 3 Ultra THV design builds upon the technical knowledge and experience gained from the SAPIEN 3 THV. CE Mark approval was received in November 2018 for patients with severe aortic stenosis and at least intermediate surgical risk, and in March 2020 for patients at low surgical risk.

This post-market study will further evaluate real-world outcomes for the SAPIEN 3 Ultra THV System in TAVI centres that are implementing minimalist periprocedural practices and facilitating early discharge home.

3 STUDY DESIGN

This is a prospective, observational, single-arm, multicentre post-market study. Up to 500 subjects who will undergo TAVI with the SAPIEN 3 Ultra THV will be enrolled at up to 50 centres predominantly in the European Union.

Clinical data and imaging available from routine clinical assessments performed pre-procedure and through 1-year post-procedure will be collected.

4 STUDY DEVICES

The study will use the following commercially available devices:

- Edwards SAPIEN 3 Ultra THV
- Edwards Commander Delivery System
- Edwards eSheath Introducer Set
- Edwards Loader
- Edwards Crimper and Crimp Stopper
- Edwards Qualcrimp Crimping Accessory

Descriptions of all study devices are provided in the respective Instructions for Use (IFU).

5 OUTCOME MEASURES

The outcome measures for the study are as follows:

- Death
- Stroke
- New requirement for permanent pacemaker
- Aortic valve reintervention
- Valve haemodynamics
 - Aortic regurgitation
 - Mean aortic valve gradient
 - Effective orifice area
- Length of index hospitalization
- Discharge location

6 STUDY POPULATION

6.1 Inclusion Criteria

Subjects must meet all of the following criteria to be included in the study:

1. Will undergo TAVI with the Edwards SAPIEN 3 Ultra System as part of standard-of-care treatment
2. Less than 80 years of age at time of the procedure
3. Low surgical risk as determined by the Heart Team
4. Meets clinical and procedural requirements for early discharge as determined by the Heart Team
5. The subject has been informed of the nature of the study, agrees to its provisions and has provided written informed consent

6.2 Exclusion Criteria

Subjects will be excluded from the study if any of the following conditions are present:

1. Medical, social, or psychological conditions that preclude appropriate consent and follow-up, including subjects under guardianship
2. Considered to be part of a vulnerable population
3. Active SARS-CoV-2 infection (Coronavirus-19 [COVID-19]) or previously diagnosed with COVID-19 with sequelae that could confound endpoint assessments
4. Cannot tolerate an anticoagulation/antiplatelet regimen
5. Active bacterial endocarditis

6. Participating in a drug or device study that has not reached its primary endpoint. Note: Participation in required national registries is not an exclusion.

7 STUDY PROCEDURES

7.1 Informed Consent

Eligible subjects who will undergo TAVI with the Edwards SAPIEN 3 Ultra THV System will be given an overview of the study. If subjects are interested in participating and are willing to authorize the use of their data, they must sign the Ethics Committee (EC)-approved informed consent form (ICF) before data collection can commence.

7.2 Data Collection

Clinical data and imaging available from routine clinical assessments performed pre-procedure and through 1-year post-procedure will be collected. Imaging obtained during this time frame should be uploaded and information entered in the CRF. It is expected that the sites' standard-of-care for the management of subjects undergoing TAVI will be aligned and consistent with established guidelines and recommendations (e.g., 2017 ESC/EACTS Guidelines for the Management of Valvular Heart Disease ³, Valve Academic Research Consortium-2 Consensus Document ⁴, echocardiographic recommendations ⁵⁻⁷) and will include, but not be limited to, the following assessments:

7.2.1 Baseline/Pre-Procedure

Data from the following assessments will be collected:

- Medical history
- Physical assessment (height and weight only)
- Risk assessment
- New York Heart Association (NYHA) functional class
- Valve-related imaging (Cardiac computed tomography angiography (CTA), transthoracic echocardiogram (TTE), transoesophageal echocardiogram (TEE), etc)

7.2.2 Procedure

The study devices will be used in accordance with the most current IFU.

The valve implant procedure will be considered to have started when the first interventional access-related puncture/incision is established. Subjects will be considered enrolled once the ICF is signed and the procedure has begun.

Data from the following assessments will be collected:

- Fluoroscopic imaging of valve deployment

- Post-deployment valve haemodynamics
- Adverse events

7.2.3 Post-Procedure Follow-up

The day of the procedure is considered Day 0 and one year is defined as 365 days.

Data from the following assessments will be collected post-procedure through 1-year (+ 60 days):

- Adverse events
- Valve-related imaging (CTA, TTE, TEE, etc.)
- Valve haemodynamics

7.3 Imaging Assessments

Imaging performed during the study should follow current guidelines and recommendations, which are noted in the imaging reference guide supplied for this trial.

7.4 COVID-19 Assessments

Results of all available SARS-CoV-2 (Coronavirus-19 [COVID-19]) testing should be recorded in the CRFs.

7.5 Subject Disposition

The following categories of subject disposition have been defined for this study:

Screen Failure: Subjects who have provided informed consent will be considered a screen failure if they do not meet the eligibility criteria or do not have the procedure started.

Enrolled: Subjects will be considered enrolled once the ICF is signed and the procedure has begun.

Discontinued: Enrolled subjects will be considered discontinued for the following reasons:

- **Study Device Never Implanted:** Subjects considered enrolled but did not receive a study valve will be exited from the study.
- **Study Device Explanted:** Subjects who have a surgical reintervention where the study valve is explanted will be exited from the study.
- **Subject Withdrew Consent**
- **Death**

If a subject discontinues, an exit form indicating the reason for discontinuation will be completed. Subjects who discontinue will not be replaced.

Complete: Enrolled subjects will be considered complete when data through 1-year post-procedure has been entered.

Table 3 summarizes the data that will be collected.

Table 3. Data Collection Schedule

Assessment	Baseline/ Pre-procedure ¹	Procedure ¹	Post-procedure through 1 Year ¹
Informed Consent	X		
Medical History	X		
Physical Assessment	X		
Risk Assessment	X		
NYHA Functional Class	X		
Valve-related Imaging ²	X	X ³	X
Valve Haemodynamics		X	X
Adverse Events		X	X

1. Results of all available SARS-CoV-2 (Coronavirus-19) testing should be recorded in the CRFs.
2. All imaging (CTA, TTE, TEE, etc.) obtained from pre-procedure through 1 year (+ 60 days) should be uploaded and information entered in the CRF.
3. Includes fluoroscopic imaging of valve deployment.

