9 RISK AND BENEFIT ANALYSIS

Subjects participating in this observational study will undergo TAVI with the SAPIEN 3 Ultra THV System as part of their standard-of-care treatment for severe AS. No study-specific procedures will be performed. There are no increased risks related to the participation in this study. There are potential risks related to the overall procedure (standard cardiac catheterization, valvuloplasty and use of anaesthesia) as well as potential risks associated with the TAVI procedure, the bioprosthesis, and the use of its associated devices and accessories; risks are summarized in the IFU.

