10 STATISTICAL CONSIDERATIONS

10.1 Analysis Populations

As Treated (AT) Population: Will consist of all subjects that were enrolled in the trial.

Valve Implant (VI) Population: Will consist of all enrolled subjects who receive and retain the study valve upon leaving the procedure room.

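### Does section 7.5 make a treated but ineligible subject both a screen failure and enrolled, leaving the As Treated population undefined?

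*Combined protocol and SAP*

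**What the plan says.** The combined protocol and SAP handles study membership in four places.

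- **Eligibility (6.1, 6.2).** "Subjects must meet all of the following criteria to be included in the study", and "Subjects will be excluded from the study if any of the following conditions are present". One inclusion criterion is dated to the procedure: "Less than 80 years of age at time of the procedure".
- **Screen failure (7.5).** A consented subject "will be considered a screen failure if they do not meet the eligibility criteria or do not have the procedure started". Either limb is enough, and the first has no time limit.
- **Enrolment (7.2.2, repeated in 7.5).** "Subjects will be considered enrolled once the ICF is signed and the procedure has begun". Eligibility is not mentioned. The procedure starts at the first access puncture or incision.
- **Analysis (10.1).** AT is defined so: "Will consist of all subjects that were enrolled in the trial". The Valve Implant (VI) population is the subset who leave the procedure room with the study valve in place.

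Section 9 adds that subjects "will undergo TAVI with the SAPIEN 3 Ultra THV System as part of their standard-of-care treatment for severe AS" and that "No study-specific procedures will be performed".

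**The concern.** In a trial that supplies the treatment, a subject who fails screening is not treated, so the two categories cannot meet. Here the valve is implanted whether or not the patient is in the study. A consented subject who turns out not to be low risk, or who is in another study, may still have the procedure. Read literally, that subject is a screen failure under 7.5, is also enrolled under 7.2.2 and 7.5, and so belongs to AT. Sections 6.1 and 6.2 say the opposite.

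Enrolment also decides VI membership, the count towards 500 and the start of adverse event capture (8.3), and up to 50 centres must apply it. If some centres followed the enrolment sentence and others the eligibility section, the pooled denominators would mix two rules. The only output is descriptive, so the denominator matters. Ineligible subjects would dilute a population meant to be under 80, at low risk and suited to early discharge.

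**Working it through.** **Step 1: the rules as logic.** For a consented subject, screen failure = not eligible OR not started; enrolled = consent signed AND started; AT = all enrolled.

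| Eligible? | Procedure started? | Screen failure | Enrolled, in AT |
|---|---|---|---|
| Yes | Yes | No | Yes |
| Yes | No | Yes | No |
| No | No | Yes | No |
| No | Yes | Yes | Yes |

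Only the last row gives two statuses.

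**Step 2: split that row by when the ineligibility is found.**

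- *Before the puncture.* Section 7.1 has eligible patients approached for consent, 6.1 and 6.2 keep others out, and the first limb of the screen failure rule names this case. The enrolment sentence says when enrolment happens; it does not say who may be a study subject. Together these give screen failure, not in AT. A subject who consents at 79 and reaches 80 before the procedure belongs here, because the date of birth and the planned date show it in advance.
- *After the puncture.* The subject is already enrolled. The discontinuation list in 7.5 has four reasons (no study valve implanted, explant, withdrawn consent, death), and ineligibility is not among them. AT has no eligibility filter. The natural reading is that the subject stays in AT and the breach is documented under 12.7. The plan does not say this outright.

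**Step 3: size if ineligible subjects did enter AT.** The documents give no frequency, so assume f = 5/500, 25/500 or 50/500 (1%, 5%, 10%). Without them the denominator would be 495, 475 or 450. Take the FAST-TAVI 30-day rates in Table 2 for eligible subjects and the higher 3M TAVR rates for ineligible ones. Both are other populations, used only for scale.

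AT rate = r_elig × (1 − f) + r_inelig × f

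| Outcome | r_elig, r_inelig | f = 1% | f = 5% | f = 10% | Largest shift |
|---|---|---|---|---|---|
| Mortality | 0.6%, 1.5% | 0.609% | 0.645% | 0.690% | 0.09 points |
| Stroke | 0%, 1.5% | 0.015% | 0.075% | 0.150% | 0.15 points |
| Pacemaker | 4.3%, 5.7% | 4.314% | 4.370% | 4.440% | 0.14 points |

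For example, pacemaker at 10%: 4.3 × 0.9 + 5.7 × 0.1 = 3.87 + 0.57 = 4.44. One event among 500 subjects is 1/500 = 0.20 points, so every shift is smaller than a single event.

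**The case for a change.** The strongest case for a change is that the contradiction can be shown from the text alone, that no sentence ranks the two statuses, and that two or three sentences would settle it without new data. Section 7.1 makes the case rarer but does not exclude it, because 7.5 itself provides for consented subjects who prove ineligible. The screen failure limb has no time limit, so someone could invoke it after treatment.

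The textual point stands, and late-found ineligibility is the part left least clear. The practical consequence is not shown. Reclassifying a treated subject as a screen failure would contradict the enrolment sentence, the discontinuation list and the AT definition together. Divergence between centres is possible, but site training may cover identifying eligible subjects (11.6), and monitoring checks compliance with the plan (11.8).

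A second argument is that early discharge, not clinical events, is where dilution would show. If no ineligible subject left within 48 hours, a rate of 89.5% would fall at f = 10% to 89.5 × 0.9 = 80.55%, a drop of 8.95 points. That bound carries little weight. The 89.5% comes from the 3M study, whose patients had a mean age of 84 and an STS score of 4.9%. On age they resemble people this study would turn away, and they still left early. If ineligible subjects did equally well, the shift would be zero. Discharge within 48 hours is also not an outcome listed in section 5. The listed ones are length of index hospitalization and discharge location, and the documents give no figures for ineligible subjects on either.

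**Conclusion.** No change follows. This is a missing precedence rule that site staff and analysts can fill from the rest of the plan: ineligible and known before the puncture means screen failure; found later means enrolled, in AT, with a deviation on file. The first reading is well supported by 6.1, 6.2 and 7.1. The second is an inference from the discontinuation list and the AT definition.

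The effect on 30-day mortality, stroke and pacemaker rates is at most 0.15 points. That rests on an assumed ineligible share of up to 10%, which is hard to square with approaching only eligible patients, and on borrowed rates. The effect on length of stay and discharge location cannot be calculated from the documents, and no bias in either is shown. Nothing inferential depends on the count: section 10.2 rules out inference, and 500 is a ceiling with no derivation, so a few subjects either way miss no power or precision target. The conclusion would be weaker if many consented subjects were found ineligible only after treatment, but nothing in the documents suggests that.

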8.3 AE Reporting Requirements

All AEs will be captured from the time of enrolment until subject participation has ended (i.e. completion of study or discontinuation). See **Section 8.3.1** for events that are not required to be reported to Edwards.

Pre-existing medical conditions or symptoms reported prior to subject enrolment will not be recorded as an AE. In the event there is a worsening in the pre-existing medical condition or symptoms due to the device or study-related procedure, then an AE must be recorded.

Death should not be recorded as an AE but should be reflected as an outcome to another specific AE.

If known, the diagnosis for an AE should be recorded, rather than listing individual signs and symptoms.

All AEs will be reported in subject medical records and the appropriate electronic case report form (eCRF) throughout the duration of the study, and will be followed until resolution, stabilization or study completion.

All SAEs and Device Deficiencies that might have led to a SAE must be reported to Edwards **immediately, but not later than 3 calendar days after site study personnel's awareness of the event.** Other AEs must be reported to Edwards as soon as practical but no later than 10 working days of awareness.

AE information must be entered into the EDC. When EDC system is not available/accessible, AE information must be reported directly via email to [contact], copying the Safety Officer of the study.

At the time of initial AE notification, the following minimal information must be provided:

- Subject ID
- AE term/diagnosis
- AE onset date
- AE seriousness
- AE device and procedure relationships

Source documentation may be requested by the Edwards Safety Officer for AEs and SAEs on a case-by-case basis (i.e., device deficiencies, device- and procedure-related events, USADEs, etc.).

The AEs will be reviewed by the Edwards Safety Officer. Each AE will be assessed as to its relationship to the study device and/or implant procedure, whether it was anticipated or not anticipated, and whether it qualifies as an SAE or USADE.

Depending on the local requirements or following agreement between both parties, Edwards or the Principal Investigator will be responsible for performing safety reporting to the EC according to the relevant local regulatory requirements.

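### Subjects with a failed implant or an explanted valve leave follow-up, so new deaths and strokes after exit go uncounted and Kaplan-Meier censoring depends on device or procedure failure; the likely effect on 1-year rates is small

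*Combined protocol and SAP*

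**What the plan says.** Under Sections 7.2.2 and 7.5 a subject counts as enrolled once consent is signed and the procedure has started, so a failed implant attempt is an enrolled subject and not a screen failure. Section 7.5 then gives two exit rules tied to the valve:

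- No valve implanted: "Subjects considered enrolled but did not receive a study valve will be exited from the study".
- Valve removed: "Subjects who have a surgical reintervention where the study valve is explanted will be exited from the study".

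The action required at exit is that "an exit form indicating the reason for discontinuation will be completed".

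Three sentences in Section 8.3 bear on what is collected:

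- The window: "All AEs will be captured from the time of enrolment until subject participation has ended (i.e. completion of study or discontinuation").
- Adverse events are reported throughout the study and "will be followed until resolution, stabilization or study completion".
- The recording of death: "Death should not be recorded as an AE but should be reflected as an outcome to another specific AE".

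Section 10.1 defines AT: "Will consist of all subjects that were enrolled in the trial". It defines the Valve Implant (VI) population: "Will consist of all enrolled subjects who receive and retain the study valve upon leaving the procedure room". Never-implanted subjects are therefore in AT only. Subjects explanted after leaving the procedure room are in both.

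Section 10.2 plans Kaplan-Meier estimates for time-to-event outcomes. It states no censoring rule and does not say which population carries the death and stroke rates.

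**The concern.** Kaplan-Meier estimation assumes that subjects censored at a given time have the same later risk as those still followed. Here two of the exit reasons are failure of the procedure or of the device, and these are the subjects for whom that assumption is least secure. If their risk after exit is higher, the 1-year death and stroke rates come out too low. If it is not higher, nothing is understated.

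Death and stroke head the list of outcome measures in Section 5, and descriptive rates are all that the study will produce. AT is the population meant to include everyone enrolled, yet it contains subjects with no planned follow-up for new events.

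**Working it through.** **No planned figure to reproduce.** The sample size is given as up to 500 without a derivation, and no inference is planned. The only event rates are the 30-day background figures in Table 2 (mortality 0.6% and 1.5%; stroke 0 and 1.5%).

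**Assumed inputs**

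- b, 1-year risk in subjects not exited: 1.5%, for death and for stroke
- f, share exited: 1.0-1.5% of AT (5 to 7.5 of 500); 0.5% of VI (explants)
- RR, risk in exited subjects relative to the rest: 3-20 for death, 1-5 for stroke; m = RR × b
- c, share of exited subjects' events that are still captured: 0, 0.5 or 0.75

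**Formulas**

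- True 1-year rate = f·m + (1 − f)·b
- Rate as the plan would estimate it = 1 − (1 − f·m·c)(1 − b), with captured events falling early and the other exited subjects censored early

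Example: f = 1.5%, RR = 20, c = 0.5, so m = 30%.

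- True = 0.015 × 0.30 + 0.985 × 0.015 = 1.9275%
- Plan = 1 − (1 − 0.00225)(0.985) = 1.7216%
- Difference = 0.206 points, or 1.03 deaths in 500

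| Outcome, population | f | RR | c | True % | Plan % | Understated (points) | Events per 500 |
|---|---|---|---|---|---|---|---|
| Death, AT | 1.0% | 3 | 0.5 | 1.5300 | 1.5222 | 0.008 | 0.04 |
| Death, AT | 1.5% | 10 | 0.5 | 1.7025 | 1.6108 | 0.09 | 0.46 |
| Death, AT | 1.5% | 20 | 0.5 | 1.9275 | 1.7216 | 0.21 | 1.03 |
| Death, AT | 1.0% | 3 | 0.75 | 1.5300 | 1.5332 | none | none |
| Death, AT | 1.5% | 20 | 0.75 | 1.9275 | 1.8324 | 0.095 | 0.48 |
| Death, AT | 1.5% | 20 | 0 | 1.9275 | 1.5000 | 0.43 | 2.1 |
| Death, VI | 0.5% | 3 | 0.5 | 1.5150 | 1.5111 | 0.004 | 0.02 |
| Death, VI | 0.5% | 20 | 0.5 | 1.6425 | 1.5739 | 0.07 | 0.34 |
| Death, VI | 0.5% | 20 | 0 | 1.6425 | 1.5000 | 0.14 | 0.71 |
| Stroke, AT | 1.5% | 5 | 0.5 | 1.5900 | 1.5554 | 0.035 | 0.17 |
| Stroke, AT | 1.5% | 5 | 0 | 1.5900 | 1.5000 | 0.09 | 0.45 |

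At RR = 1 there is no understatement.

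**Later explants.** The formula places exits near Day 0. Take instead an explant at 6 months with nothing captured after exit and risk q over the remaining half-year. With h = b/2 and k = h/(1 − h), the true rate is h + (1 − h − f)·k + f·q, against b from Kaplan-Meier. For b = 1.5%, f = 1% and q = 30%, that is 1.79% against 1.50%, a gap of 0.29 points. Over b of 1.5-3%, f of 0.5-1% and q of 10-30%, the gap is 0.04-0.29 points.

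**Wider assumptions.** With exits near Day 0 and nothing captured, the gap is f(q − b). For f = 3% and q = 30% it is 0.88 points at b = 0.6%, 0.855 at 1.5% and 0.81 at 3%. In the first case the true rate is 1.48% against a reported 0.60%, so about 60% of the true rate is missed.

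**Scale.** The standard error of 1.5% in 500 is √(0.015 × 0.985/500) = 0.54 points. Eight deaths in 500 has an exact 95% interval of 0.69% to 3.13%.

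**The case against.** Five arguments can be made for the plan.

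- **Censoring at exit is inferred.** Section 10.2 does not state it, and Section 7.5 does not date the exit. This is true, but with no data after exit a Kaplan-Meier analysis has nowhere else to censor.
- **Failure-related deaths may be caught.** They tend to come early. Death is its own discontinuation category in Section 7.5, and adverse events already open are to be followed to resolution, stabilization or the end of the study. This stands in part, and it is why half and three-quarters capture are included above. It does not cover new events, and it does not fit a capture window that closes at discontinuation.
- **The study is about the device.** After a failed implant or an explant, later events partly reflect other treatment, and VI already leaves out never-implanted subjects. That is a fair reading of the objective, but AT includes every enrolled subject and VI keeps the later explants.
- **The exits are documented.** The exit form gives the reason, an explant counts as aortic valve reintervention, explanted valves go to histopathology (Section 11.5), and the difference between AT and VI shows most early implant failures. All of this stands. It records the failure, not what happens to the subject afterwards, and the plan does not commit to tabulating exits by reason and time.
- **The effect is small and its size is assumed.** This stands, and it sets the severity.

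**Conclusion.** The concern holds as a minor point. The structural part follows directly from Sections 7.5, 8.3, 10.1 and 10.2: new deaths and strokes after these exits are not collected, and censoring depends on device or procedure failure.

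The size does not come from the documents. If about 1.0-1.5% of AT are exited and half of their deaths are captured, AT mortality is understated by 0.01 to 0.21 points, at most about one death in 500 and well inside sampling error. The most in that range of exits is 0.43 points, at a risk ratio of 20 with nothing captured. Stroke and VI effects are smaller. If exits reached 3% with a post-exit risk of 30% and no capture, the gap would approach 0.9 points, so a small effect is likely but not assured. The study makes no formal comparison that this could overturn.

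**What to change.** - **Section 7.5:** keep never-implanted and explanted subjects in follow-up for death and stroke from routine-care data through 1 year. Stop only the study-valve haemodynamics.
- **Section 8.3:** reconcile the capture window that ends at discontinuation with the sentence on following adverse events, and say which applies to these subjects.
- **Section 10.2:** report death and stroke in AT. Censor at consent withdrawal, last contact or day 365. For stroke, also censor at death or treat death as a competing event. Tabulate exits by reason and time.
- **If post-exit data cannot be obtained:** an optional analysis can count every exited subject as an event, labelled as an extreme upper bound and not an estimate. It gives f + (1 − f)·b = 2.49% at f = 1.0% and 2.98% at f = 1.5%, that is 0.99 and 1.48 points above 1.5%.

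The cost is wording in three sections plus routine-care death and stroke data on about 5 to 8 subjects (1.0-1.5% of 500, assumed), with no added procedures. Section 12.6 requires ethics committee approval at each site, with up to 50 centres, so the change is best combined with another amendment. Reported rates may look slightly less favourable.
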